10. APPENDICES

10.1. Appendix 6: Derived and Transformed Data

10.1.1. General

Study Day

- Study Day 1 is defined as the day the first dose was taken.
- Study Day > 1 is calculated as the number of days that have passed since the date when the first dose was taken (Study Day 1):
 - Ref Date = Missing → Study Day = Missing
 - Ref Date < Date of Study Day 1 → Study Day = Ref Date Date of Study Day 1
 - Ref Data ≥ Date of Study Day 1 → Study Day = Ref Date (Date of Study Day 1) + 1

10.1.2. Handling of Missing Data

Element	Reporting Detail	
General	Missing data occurs when any requested data is not provided, leading to blank fields on the collection instrument:	
	 If only some of the values within the test are missing, those fields will be marked as "blank". Otherwise, if all data for a specific visit are missing, the data will be completely excluded from the table. Answers such as "Not applicable" and "Not evaluable" are not considered to be missing data and should be displayed as such. 	
Outliers	• Any participants with outlying results may be excluded in additional ad hoc summaries and/or statistical analyses. These will be documented along with the reason for exclusion in the clinical study report, but the primary conclusions will remain based on the full population sets.	

10.1.2.1. Handling of Missing Data for Statistical Analysis

Element	Reporting Detail
efficacy endpoints	• For all analyses of the Efficacy analysis set, missing value imputation will not be performed and participants' data will be excluded from any statistical analyses due to missing data.

10.2.2.2 Multiple measurements at One Analysis Time point

Element	Reporting Detail
efficacy and safety endpoints	• For all analyses of the Efficacy and safety, last non-missing measurement will be flagged for summary and statistical analysis at any post-baseline visit. If listed, all data will be presented

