- Measure vital signs including respiratory rate, body temperature, blood pressure, pulse rate, oxygen saturation and weight.
- Collect laboratory samples, including Comprehensive Metabolic Panel (CMP), Complete Blood Count (CBC), Coagulation Panel and Urine pregnancy test if female of childbearing potential.
- Physical examination by Principal Investigator, including clinical assessments such as MDS-Unified Parkinson's Disease Rating Scale and other assessments included in Table 3.
- Completion of neuro-quality of life questionnaire by study participant and handwriting assessments.
- Investigational product administration by delegated study personnel. HB-adMSCs or Placebo should only be administered intravenously, with a dosing rate of 4-5ml/min and a vital sign monitoring of two hours post-drug exposure. Monitoring time may be prolonged if decided by principal investigator. Vital signs must be monitored as follows:

- A video documenting study participant walking and standing from sitting will be recorded during this visit. However, if the period of time between Visit 1 Screening and Visit 2 Infusion 1 (Baseline) is less than 10 days, the video does not need to be repeated.
- 24 hours after administration of the investigational product, study participants will be contacted by telephone call to assess the incidence of adverse events.

Visit 3, 4, 5 6, and 7 – Infusions 2, 3, 4, 5 and 6

- Update medical history and concomitant medications if any change occurred since last visit.
- Measure vital signs including respiratory rate, body temperature, blood pressure, pulse rate, oxygen saturation and weight.
- Physical examination by Principal Investigator, including clinical assessments such as MDS-Unified Parkinson's Disease Rating Scale and other assessments included in Table 3.
- Completion of neuro-quality of life questionnaire by study participant and handwriting assessments.
- Collection of laboratory samples, including Comprehensive Metabolic Panel (CMP), Complete Blood Count (CBC), Coagulation Panel and Urine pregnancy test if female of childbearing potential (only during Visit 6, Infusion 5)

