- Investigational product administration by delegated study personnel: HB-adMSCs or Placebo should only be administered intravenously with a dosing rate of 4-5ml/min and vital sign monitoring of two hours post-drug exposure. Monitoring time may be prolonged if decided by principal investigator. The monitoring of vital signs shall be the same as represented in Figure 8.
- 24 hours after administration of the investigational product, study participants will be contacted by telephone call to assess the incidence of adverse events.

Visit 8 – Safety Follow Up

- Update medical history and concomitant medications if any change occurred since last visit.
- Measure vital signs including respiratory rate, body temperature, blood pressure, pulse rate, oxygen saturation and weight.
- Physical examination by Principal Investigator, including clinical assessments such as MDS-Unified Parkinson's Disease Rating Scale and other assessments included in Table 3.
- Completion of neuro-quality of life questionnaire by study's participant and handwriting assessments.
- Assess the incidence of any adverse event since last visit.

Visit 9 – End of Study

- Update medical history and concomitant medications if any change occurred since last visit.
- Measure vital signs including respiratory rate, body temperature, blood pressure, pulse rate, oxygen saturation and weight.
- Physical examination by Principal Investigator, including clinical assessments such as MDS-Unified Parkinson's Disease Rating Scale and other assessments included in Table 3.
- Completion of neuro-quality of life questionnaire by study's participant and Handwriting assessments.
- Collection of laboratory samples, including Comprehensive Metabolic Panel (CMP), Complete Blood Count (CBC), Coagulation Panel and Urine pregnancy test if female of childbearing potential.
- A video documenting study participant walking and standing from sitting will be recorded during this visit.
- Assess the incidence of any adverse event since last visit.

Unscheduled Visits

The Investigator may at his/her discretion arrange for a study participant to have an unscheduled visit (UNS). Some of the circumstances by which a study participant will be called for a UNS visit are:

- Adverse events (AEs) that require follow-up.
- Collection of laboratory samples for safety reasons.
- Procedures missed at previous study visits.

All unscheduled visits should be documented in the study's participant source.

Trial Assessments

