5.2 Baseline Definitions

For all endpoints, the baseline value will be the value obtained at the latest pre-treatment assessment visit (a non-missing value), including those from unscheduled visits. For example, if an assessment has been made both at screening visit (Visit 1) and infusion 1 visit (listed as Visit 2, Week 0), the value from the later, "infusion 1 visit" is used as the baseline value, if the value is collected prior to the admission of infusion. If the value measured at the Week 0 visit is missing or if it was collected on/after the dose and the assessment has been made at screening/unscheduled visits (which is prior to Week 0 visit), then the screening/unscheduled visits value is used as the baseline value.

Unless otherwise stated, if baseline data is missing, no derivation will be performed, and baseline will be set to missing.

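### Read literally, the last-value rule in SAP 10.2.2.2 makes the by-visit vital signs at Weeks 4 to 32 post-infusion readings, set against a pre-infusion baseline

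*SAP*

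**What the plan says.** **Selection rule.** SAP 10.2.2.2 applies to efficacy and safety endpoints alike: the "last non-missing measurement will be flagged for summary and statistical analysis at any post-baseline visit". It adds "If listed, all data will be presented".

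**Baseline.** Under SAP 5.2, "the baseline value will be the value obtained at the latest pre-treatment assessment visit". A Week 0 value counts only "if the value is collected prior to the admission of infusion".

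**Readings at an infusion visit.** The protocol takes vital signs at all nine visits. At Visit 2 (Infusion 1) the product is given "with a dosing rate of 4-5ml/min and a vital sign monitoring of two hours post-drug exposure". The section on Visits 3 to 7 (Infusions 2 to 6) repeats the "vital sign monitoring of two hours post-drug exposure". It adds "Monitoring time may be prolonged if decided by principal investigator" and, for the reading times, "The monitoring of vital signs shall be the same as represented in Figure 8". That figure is not in the public text.

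**Vital-sign summaries.** SAP 8.3 plans descriptive summaries by visit and as change from baseline, plus individual listings. It does not separate readings before and after the infusion.

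**Endpoints.** SAP section 2 sets the clinical-parameter endpoint, including pulse and systolic blood pressure, as the change to Week 52. The protocol's Secondary Endpoints also name clinically significant vital-sign changes at Weeks 4, 8, 16, 24, 32, 42 and 52.

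**The concern.** A change from baseline is easiest to interpret when both readings are taken under the same conditions. Here the baseline must precede the infusion, while the rule would select a reading taken after 250 ml of fluid and about two hours of observation. At Weeks 42 and 52 nothing is infused. A shift in the series between Week 32 and Week 42 could then reflect the end of infusions rather than any lasting change in the patient.

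A second loss concerns acute effects. The protocol's infusion stopping rules treat a fall from the pre-infusion level as the acute signal, but the SAP derives no change from the same visit's pre-infusion reading. The saline volume is common to both arms. An acute effect of the cells would not be, and no summary described in the SAP text is built to compare the arms on it. A modest shift in one arm, below what an investigator would call clinically significant, would be visible only by reading the listings.

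**Working it through.** The plan states no figure for this point, so there is none to reproduce. The check applies the rule to the visit schedule.

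**1. Visits affected.**
- Infusion visits (protocol Study Summary): Weeks 0, 4, 8, 16, 24, 32, which is 6.
- Post-baseline visits: Weeks 4, 8, 16, 24, 32, 42, 52, which is 7.
- In both lists: Weeks 4, 8, 16, 24, 32, which is 5.
- The rule therefore reaches 5 of 6 infusion visits and 5 of 7 post-baseline visits. Week 0 is the baseline visit and lies outside a post-baseline rule. Its post-infusion readings enter no change-from-baseline summary at all.

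**2. Timing of the selected reading.**
- Inputs: 250 ml at 4 to 5 ml/min (Treatment Regimen) and 120 min of monitoring.
- Infusion time = volume / rate: 250/5 = 50 min to 250/4 = 62.5 min. This agrees with the 1 hour in the Study Summary.
- End of monitoring = infusion time + 120: 170 to 182.5 min after the infusion starts, later if monitoring is prolonged. This assumes that a reading is taken at the end of the two hours.

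**3. What each week's value represents.**

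| Visit | Value used under the literal rule | Condition |
|---|---|---|
| Week 0 | Latest pre-treatment value | Before infusion |
| Weeks 4, 8, 16, 24, 32 | Last reading of the visit | After infusion, end of monitoring |
| Weeks 42, 52 | Last reading of the visit | No infusion |

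**4. How much of a short-lived change would remain (illustration only).** The documents give no recovery profile. Assume a change of 30 to 40 mmHg, the size of fall named in the Infusion Stopping Rules, present at the end of infusion and decaying exponentially. The part left 120 min later is peak × 0.5^(120/half-life).

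| Assumed half-life | Left from 30 mmHg | Left from 40 mmHg |
|---|---|---|
| 15 min | 0.1 | 0.2 |
| 30 min | 1.9 | 2.5 |
| 60 min | 7.5 | 10 |
| 120 min | 15 | 20 |

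The half-lives and the timing of the peak are assumptions. The table shows that the by-visit value could keep almost none, or about half, of an early change. It does not say which applies here.

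**The case against.** The strongest reply is that 10.2.2.2 is only a tie-break. Its title speaks of a single analysis time point, and the protocol lists the routine vital-sign measurement and the post-infusion monitoring as separate procedures. On that reading, monitoring values are not repeats of the visit value. The reading times are in a figure, and the SAP's planned displays are in an appendix, neither of which is in the public text, so separate time points may exist there. This makes the narrower reading possible. It does not settle the matter: the operative sentence refers to the visit, and the SAP text defines no time point within it. A programmer would have to guess.

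The second reply is that acute changes have other routes, and this largely stands. Individual vital signs are listed, which is manageable with 24 subjects. Clinically significant abnormal findings become adverse events and are summarised as such. Several infusion stopping rules act on vital signs at the bedside. A reader might infer that the plan conceals acute reactions; the documents do not support that. What is missing is a by-arm summary of changes that nobody judged clinically significant.

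A reader might also infer that the last reading is always the most recovered one. The documents do not say so, and a reaction with later onset would be largest at the end of monitoring.

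**Conclusion.** The point holds as a cheap improvement. Taken literally, the SAP puts post-infusion values at Weeks 4, 8, 16, 24 and 32 into the same change-from-baseline series as infusion-free values at Weeks 42 and 52, all against a pre-infusion baseline. It also leaves the other monitoring readings out of the summary tables, including every post-infusion reading at Week 0.

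Three limits apply:
- Not every infusion visit is affected. Infusion 1 is the baseline visit, so the count is five of six.
- It is tempting to conclude that the primary safety endpoint is compromised. The primary vital-sign comparison is at Week 52, where nothing is infused, and it is untouched. The affected weeks matter through the protocol's secondary endpoint and the by-visit tables, which are descriptive.
- The size of any shift cannot be obtained from the documents.

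The conclusion assumes that monitoring readings are recorded as data for the visit, and that no unseen display or figure gives them their own analysis time points.

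**What to change.** Add one sentence to SAP 10.2.2.2 or 8.3: for vital signs, infusion visits are exempt from the last-value rule, and the visit value is the reading taken before that visit's infusion. The protocol lists the routine measurement ahead of product administration but does not state its timing, so the sentence should define the pre-infusion reading explicitly. The rule can stay as it is for other data.

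Add one descriptive table, by arm and visit, of the largest change from the same visit's pre-infusion reading during monitoring. Cover all six infusions, including Week 0, and use the readings as recorded. No hypothesis test is needed, and no clinical procedure changes.

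The cost is one sentence and one table. The table is possible only if the monitoring readings are captured in the database, ideally with their times. Neither document confirms this, so it should be checked first. If they are not captured, the sentence on the visit value is still worth adding.
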